4.2. SECONDARY ENDPOINTS

- Domain scores and item responses at key QoL host trial time points.
- Compliance with questionnaire completion at all further time points of QoL collection within the host trial.
- Completeness of data (% of questions filled in within the questionnaire) in the host trial's primary QoL questionnaire.
- Patient satisfaction with electronic and paper questionnaires.
- Patient demographics in each group
- Change in response scores from baseline.
- Time taken (minutes) to prepare a paper questionnaire for distribution compared to electronic dispatch.
- % of patients sent reminders to complete questionnaires for paper and electronic questionnaires.

4.3. FEASIBILITY ENDPOINTS

- The number of participants opting for a preference rather than randomisation after 50 patients have enrolled.
- The number of participants enrolled after 6 months.

5. PATIENT SELECTION & ELIGIBILITY

5.1. NUMBER OF PARTICIPANTS

Two-hundred and forty-four randomised participants are required to detect non-inferiority of electronic PRO questionnaires compliance compared to paper with a 10% non-inferiority margin i.e. at most 10% worse compliance. We have assumed that approximately two-thirds of patients entering the SWAT will agree to be randomised thus anticipate needing to recruit approximately 366 patients overall.

5.2. SOURCE OF PARTICIPANTS

Participants will be recruited from ICR-CTSU clinical trials hosting the SWAT from participating NHS sites in the UK. Potential participants will be identified by their clinical care/research teams during the process of assessment for eligibility for an ICR-CTSU host trial.

5.3. INCLUSION CRITERIA

1. Participation in a host trial
2. Participation in host trial's QoL/PRO sub study (if applicable - format A only)
3. Informed consent for participation in SPRUCE

4. Ability to read English

5.4. EXCLUSION CRITERIA

None

5.5. PROCEDURE FOR OBTAINING INFORMED CONSENT

The Principal Investigator (or designated individual) must ensure that each study participant is fully informed about the nature and objectives of the study and possible risks associated with participation. Participants should be given the current ethics approved SPRUCE patient information sheet for their consideration. Patients should only be asked to consent to the study after they have had sufficient time to consider the information, and the opportunity to ask any further questions.

Patients who are unwilling to be randomised should be offered participation in the patient preference cohort. Refusal to participate in the SPRUCE study will not result in ineligibility to participate in the host trial.

Confirmation of the patient's consent and the informed consent process must be documented in the patient's medical notes. A copy of the signed consent form should be provided to the patient and the original retained in the investigator site file, which must be available for verification by ICR-CTSU study staff or for regulatory inspection at any time.

5.6. PARTICIPATION IN OTHER CLINICAL TRIALS

As SPRUCE is a SWAT participants in SPRUCE will already be enrolled in a host ICR-CTSU trial. Participants in ICR-CTSU host trials will be able to participate in further clinical trials in accordance with the host trial protocol.

6. STUDY ENTRY

Patients must be centrally enrolled onto the study by the trials unit (ICR-CTSU) following informed consent.

Patients should be enrolled onto the study by emailing ICR-CTSU on:
[contact]
and requesting a call back
09.00-17.00 (UK time) Monday to Friday

Patients will either be randomised between paper and PRO completion or registered to complete questionnaires in their preferred format. A study entry checklist must be completed prior to randomisation.

The following information will be required at study entry:

- Name of hospital, consultant and person registering patient
- Confirmation that patient has given written informed consent for study
- Confirmation that patient is eligible for the study
- Whether the patient has consented to being randomised to either paper or electronic questionnaires
- Preferred modality of PRO completion if patient has not consented to be randomised
- ICR-CTSU host trial name, host trial ID and date of enrolment onto the host trial
- Host trial treatment start/end date (if available)
- Patient's full name, postal address, email address (if applicable/available), sex and date of birth

The caller will be given the patient's unique study number (study ID) and questionnaire format allocation.

ICR-CTSU will send confirmation to the recruiting site to confirm patients' entry into the study.

Participants completing their questionnaires electronically will be provided with participant electronic questionnaire guidance for using the electronic system.

7. STUDY ASSESSMENTS

7.1. PRIOR TO STUDY ENTRY

All participants should complete their baseline questionnaire booklet on paper.

For format A studies the host trial's approved baseline booklet should be completed by SPRUCE participants as part of the host trial entry procedure and in accordance with instructions in the host trial's protocol.

7.2. FOLLOW UP

Follow up questionnaires will be administered at time points determined by the host trial for format A and B, as described in the trial specific appendices.

Questionnaires will be administered for the purposes of the SPRUCE study up to 12 months post study entry, after which PRO data will continue to be collected within the host trial as appropriate.

7.3. DEMOGRAPHICS QUESTIONNAIRE

Participants will be sent a demographics questionnaire after study entry in their chosen/allocated format.

7.4. POST-QUESTIONNAIRE FOLLOW UP

Participants will receive a paper questionnaire regarding satisfaction with questionnaire method at 14 months after study entry.

7.5. DISCONTINUATION OF PARTICIPATION

Participants may discontinue from participation in SPRUCE at any time at their own request. Participants who cease participation will continue to be followed up in the QoL sub study within the host trial for format A, unless they specify otherwise.

8. STATISTICAL CONSIDERATIONS

8.1. STATISTICAL DESIGN AND SAMPLE SIZE JUSTIFICATION

This is a partially randomised patient preference study, allowing participants to choose a preferred modality for questionnaire completion if they are unwilling or unable to be randomised between electronic or paper questionnaires. The randomised and patient preference groups will be analysed separately.

Sample size estimates are based on numbers required for the randomised part of the study. Based on compliance reports from existing ICR-CTSU trials, return rates for paper questionnaires are expected to be in the region of 90% at the first post intervention time point. 244 patients would therefore be required to be randomised (1:1) to exclude $\leq 80\%$ compliance rates with ePRO (i.e. 10% non-inferiority margin), with 80% power and 1-sided $\alpha=0.05$.

We have assumed that approximately two-thirds of patients entering the SWAT will agree to be randomised thus anticipate needing to recruit 366 patients overall (244 randomised and 122 preference).

The proportion of participants opting for allocation via randomisation versus preference will be monitored throughout SPRUCE; if the numbers in the randomisation cohort are lower than anticipated then the study design may be changed to offer all patients the choice of electronic or paper questionnaires (see Section 8.4).

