1. INTRODUCTION

Within healthcare and clinical trials, questionnaires can be used to collect information directly from patients on the impact that treatment and health conditions may be having upon their quality of life. These data are known as patient reported outcomes (PRO) and are defined as “any report of the status of a patient’s health condition that comes directly from the patient, without interpretation of the patient’s response by a clinician or anyone else”(1). A wide range of validated questionnaires are used to collect PRO, covering general health items as well as more disease specific factors.

Within oncology trials, the patient perspective and survivorship effects are crucial factors to consider in evaluation of new treatments (2). Quality of life (QoL) information is thus a key factor to consider in their adoption and implementation. At many clinical trials units, including the Institute of Cancer Research Clinical Trials Statistical Unit (ICR-CTSU), QoL information is currently captured with paper PRO questionnaires to inform primary and key secondary end points of clinical trials. Collection of PROs is a time consuming and laborious process requiring significant input from both patients, hospital staff and clinical trials units often over an extended period of time. Streamlining this process with the use of technology in the form of electronic PRO (ePRO) questionnaires has the potential to increase patient convenience, improve patient experience, reduce administrative burden, save costs, increase patient compliance and avoid secondary data errors including those due to data transcription, leading to more accurate and complete data (3)(4).

Over the past decade, advances in information technology and improved access to the internet have led to a rapid increase in the use of electronic devices including smartphones, tablets and laptops. In 2019 91% of adults in the UK had regular use of the internet (5), with the over 65s having a striking increase in internet use from 2011 to 2019. The effect of the COVID-19 crisis is likely to have increased internet exposure further and it has already been shown that the proportion of online adults aged over 65 who make a least one video-call each week increased from 22% in February 2020 to 61% by May 2020 (6).

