8.2. QUESTIONNAIRE FORMAT ALLOCATION

Participants providing written informed consent will first be asked if they agree to being randomised between the two groups. If they agree they will be randomised 1:1 based on minimisation factors of age and sex and host trial to receive either electronic or paper questionnaires. A minimum of two and a maximum of six host trials will be included. The minimisation algorithm used in ICR-CTSU has a random element.

If participants do not agree to be randomised they can take part in the study in the group of their choice i.e. paper or electronic questionnaires and the reason for refusing randomisation/preferring one format will be recorded.

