8.3. STATISTICAL ANALYSIS PLAN

The randomised and patient preference cohorts will be analysed separately for all endpoints as confounders including patient baseline characteristics (e.g. age, sex) will need to be taken into account for the comparisons between electronic and paper questionnaires in the non-randomised patients. Regression analyses will adjust for potential confounders such as patient demographics and clinical characteristics for the comparison of outcomes between the patient preference groups. Additionally, descriptive analyses will summarise demographic and clinical characteristics of patients opting for randomisation versus expressing a preference.

The primary outcome of compliance at the first post intervention time point within the host trial will be calculated as percentage of returned questionnaires out of those expected (i.e. not withdrawn or died) for the electronic and paper questionnaire groups, and the difference calculated along with a 2-sided 90% confidence interval. Non-inferiority for electronic questionnaires will be concluded if the lower confidence limit for the difference in compliance for electronic versus paper questionnaires is greater than -10%.

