8.4. INTERIM ANALYSES AND STOPPING RULES

The number of patients opting for a preference rather than allocation via minimisation will be monitored monthly and assessed after 50 patients have been recruited. If greater than 50% of participants have declined allocation via minimisation, or subsequently declined allocated modality, consideration will be given to ceasing randomisation and adopting an alternative recruitment and analysis strategy.

The overall feasibility of recruitment for the study will be monitored and re-evaluated if a third of the required patients have not been recruited within 6 months of the study commencing. If recruitment was an issue at that point, the decision to increase the number of sites that the SWAT is run at or to embed the SWAT into further ICR-CTSU trials could be taken to improve recruitment.

Impact of SPRUCE on PRO uptake and drop out in host trials will be monitored to ensure that PRO data collection within the host trial is not adversely affected by the SWAT. Under format A this will consider the number/proportion of patients consenting to provide PRO data pre and post implementation of SPRUCE.

An interim analysis to review emerging data is planned between 12-18 months after the trial opens and will include the facility to include data in a confidential PhD thesis. Analyses will follow the main statistical analysis plan, although may be largely descriptive if the number of patients are insufficient for formal statistical analysis. Results will be confidential and only for the purposes of the PhD.

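### The adjusted electronic-versus-paper comparison in the preference cohort includes people who could only use paper, so it cannot separate modality from digital access

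*Protocol*

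**What the plan says.** Section 8.1 opens the preference cohort to participants "if they are unwilling or unable to be randomised between electronic or paper questionnaires". Section 8.2 says of those who do not agree to randomisation that "they can take part in the study in the group of their choice i.e. paper or electronic questionnaires", and that "the reason for refusing randomisation/preferring one format will be recorded". Neither the inclusion criteria (5.3) nor the exclusion criteria (5.4) require email or internet access, and the study-entry list in section 6 asks for an "email address (if applicable/available").

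On analysis, section 8.1 states: "The randomised and patient preference groups will be analysed separately". Section 8.3 acknowledges confounding in the preference cohort and plans for it: "Regression analyses will adjust for potential confounders such as patient demographics and clinical characteristics". For the satisfaction and demographic summaries, 8.3 names three groups only: the randomised, those who chose electronic and those who chose paper.

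Section 8.4 sets a review after 50 recruits: "If greater than 50% of participants have declined allocation via minimisation, or subsequently declined allocated modality", ceasing randomisation is to be considered.

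**The concern.** The preference cohort can hold two kinds of paper user: those who could have used either format and chose paper, and those for whom electronic completion was never possible. The protocol gives no rule for separating them, and its group labels leave the second kind nowhere to go but the paper group.

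The planned regression needs people with similar characteristics in both formats. A person without access has no chance of being in the electronic group, so this condition fails for that subgroup. Any difference in return rate, completeness or scores between the preference groups would then be part modality and part digital access.

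The cohort is analysed for every endpoint. In addition, 8.1 and 8.4 allow randomisation to be dropped in favour of offering everyone a choice. If that happened, this comparison would carry more of the study's evidence.

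**Working it through.** **1. What is not affected.** Inputs from 8.1: 90% return on paper, 10-point margin, 80% power, one-sided alpha 0.05, 1:1 allocation; equal electronic return is assumed. With the Farrington-Manning variance, the restricted rates under the null are 0.831 and 0.931.

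- Null variance: 0.831 × 0.169 + 0.931 × 0.069 ≈ 0.204
- Variance under the alternative: 2 × 0.9 × 0.1 = 0.18
- n per arm = (1.645 × √0.204 + 0.842 × √0.18)² / 0.10² ≈ 121.1, rounded up to 122, so 244 in total
- Total enrolment: 244 / (2/3) = 366, leaving 122 in the preference cohort

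The stated figures reproduce. None depends on how people are classified within the preference cohort.

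**2. How many could lack access (assumption).** The documents give no rate for this population. The Introduction says "In 2019 91% of adults in the UK had regular use of the internet". Take the complement, 9%, and assume that all such people enter the preference cohort.

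- 0.09 × 366 = 32.9, about 33 people
- Share of the preference cohort: 32.9 / 122 = 27%
- Share of the paper group: 32.9 / 122 = 27% if the whole cohort is on paper; 32.9 / 61 = 54% if half is

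**3. Effect on the paper group's rate.** Let u be the no-access share of the paper group and d the difference in return rate between no-access participants and the other paper users. The paper rate is then the rate among those who had a choice plus u × d. The documents give neither u nor d. For illustration:

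| d (assumed) | u = 27% | u = 54% |
|---|---|---|
| −10 points | −2.7 points | −5.4 points |
| +5 points | +1.4 points | +2.7 points |

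The sign is open: people without access might return less, or, being used to paper, more.

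**4. Why a further covariate does not solve it.** The covariate examples in 8.3 do not name access. If an access indicator were added, no electronic participant would lack access, so that subgroup could say nothing about electronic versus paper. The modality contrast would rest on people with access, which amounts to restriction by another route. It is clearer to restrict openly.

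**5. The refusal trigger.** More than 50% of 50 means at least 26. At the planned one-third not randomised, the probability of reaching 26 is 0.5%. Suppose 10% are unable and one-third of the rest decline: the share not randomised is 0.10 + 0.90/3 = 40%, and the probability is 5.7%. With 20% unable, the share is 0.20 + 0.80/3 = 47% and the probability 26.9%. That increase reflects people who really are unavailable for randomisation.

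Now suppose 10 of 50 are unable and 18 decline. The share not randomised is 28/50 = 56%, which triggers review. Leaving the unable out gives 18/40 = 45%, which does not, although 22/50 × 366 ≈ 161 randomised would fall well short of 244.

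**The case against.** The protocol already calls this cohort confounded, analyses it apart from the randomised cohort and draws no non-inferiority conclusion from it. The covariate list is open-ended, further analysis detail is left to a statistical analysis plan, and the recorded reason makes people without access identifiable in principle. Nor does 8.1 mention inability to use the electronic format; lack of access is only the most evident example of being unable to be randomised.

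Much of this stands. It keeps the point secondary, and it means the problem can be repaired from data already planned. It does not remove the point: 8.3 does fix the method for this comparison, that method cannot work for people with only one possible format, and the recorded reason is given no role in the analysis. A blank email field would not identify them either, since it may mean either that the person has no address or that none was needed.

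Three stronger readings are tempting but unsupported:

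- **That the refusal trigger is biased and people without access should be left out of it.** The trigger guards the number who can be randomised, and people who cannot be are a true loss. Removing them could hide a shortfall, as step 5 shows. It also leads only to consideration of a change. At most, its wording leaves unclear whether an unable person counts as having declined.
- **That the distortion approaches half the non-inferiority margin.** The margin belongs to the randomised comparison, which is untouched, and the size rests on assumed access and return rates.
- **That the demographic comparison between groups is biased.** Describing how those groups differ is a stated objective (2.2), and differences in access are part of what it may show.

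**Conclusion.** The point holds for one analysis: the adjusted electronic-versus-paper comparison within the preference cohort. As planned, it mixes modality with digital access, and covariate adjustment cannot supply the missing electronic users.

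The size cannot be derived from the documents. The 27% to 54% share of the paper group rests on three assumptions: that a figure for all UK adults in 2019 carries over to these trial participants, that everyone without access joins SPRUCE and enters the preference cohort, and that between all and half of that cohort is on paper. People without access may instead decline SPRUCE, which would lower the share; an older oncology population could raise it. The resulting shift in return rate could go either way.

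This is a cheap improvement to a secondary analysis and does not threaten the trial's main conclusion.

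**What to change.** - **Section 8.2:** add no usable email or internet access as a coded category of the reason already recorded, completed at study entry.
- **Section 8.3:** restrict the adjusted electronic-versus-paper preference comparison to participants able to use either format, and describe the no-access group separately.
- **Section 8.4:** keep the trigger on all enrolled participants and say that those unable to be randomised count towards it. At the 50-patient review, also report how many were unable and how many unwilling.

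The cost is one coded item and a few sentences. The downside is a smaller adjusted comparison: under the 9% assumption, about 122 − 33 = 89 people instead of 122. No sample-size figure changes.

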8.2. QUESTIONNAIRE FORMAT ALLOCATION

Participants providing written informed consent will first be asked if they agree to being randomised between the two groups. If they agree they will be randomised 1:1 based on minimisation factors of age and sex and host trial to receive either electronic or paper questionnaires. A minimum of two and a maximum of six host trials will be included. The minimisation algorithm used in ICR-CTSU has a random element.

If participants do not agree to be randomised they can take part in the study in the group of their choice i.e. paper or electronic questionnaires and the reason for refusing randomisation/preferring one format will be recorded.

8.3. STATISTICAL ANALYSIS PLAN

The randomised and patient preference cohorts will be analysed separately for all endpoints as confounders including patient baseline characteristics (e.g. age, sex) will need to be taken into account for the comparisons between electronic and paper questionnaires in the non-randomised patients. Regression analyses will adjust for potential confounders such as patient demographics and clinical characteristics for the comparison of outcomes between the patient preference groups. Additionally, descriptive analyses will summarise demographic and clinical characteristics of patients opting for randomisation versus expressing a preference.

The primary outcome of compliance at the first post intervention time point within the host trial will be calculated as percentage of returned questionnaires out of those expected (i.e. not withdrawn or died) for the electronic and paper questionnaire groups, and the difference calculated along with a 2-sided 90% confidence interval. Non-inferiority for electronic questionnaires will be concluded if the lower confidence limit for the difference in compliance for electronic versus paper questionnaires is greater than -10%.

For the secondary outcomes of questionnaire compliance at further time-points and data completeness, percentages between groups at each time-point will be tabulated. Questionnaire domain scores will be calculated as per guidance for each specific measure (e.g. the global health/overall quality of life score from the EORTC QLQ-C30), and compared between electronic questionnaires and paper questionnaires at each time-point using descriptive statistics appropriate for the distributions (e.g. means or medians for numeric scales and percentages for categorical outcomes). Completeness of data and change in domain scores from baseline will be calculated for each follow-up time point, and described between the electronic and paper questionnaire groups. Patient satisfaction with each questionnaire modality and patient demographics across groups (randomised, chose electronic and chose paper) will be captured via patient completed questionnaire and summarised descriptively. Time taken to distribute questionnaires and proportion of reminders sent will also be described. Where appropriate further statistical tests will be used to compare electronic and paper groups for the secondary endpoints including t-tests or Mann-Whitney tests for continuous data. For ordinal data, the chi-squared test for trend will be used. Chi-squared tests will be used for categorical data; Fisher's exact will be used if assumptions of chi-squared are not met.

Further details of analysis methods will be specified in a Statistical Analysis Plan in accordance with ICR-CTSU Standard Operating Procedures.

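### The primary non-inferiority comparison is specified as a crude difference although allocation is minimised on age, sex and host trial; the cost is small and on the conservative side

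*Protocol*

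**What the plan says.** Protocol section 8.2 says of participants who accept randomisation that "they will be randomised 1:1 based on minimisation factors of age and sex and host trial". It adds that the algorithm has a random element and that two to six host trials will be included.

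Section 8.3 defines the primary outcome as the percentage of expected questionnaires returned in each modality group, "and the difference calculated along with a 2-sided 90% confidence interval". Non-inferiority follows if the "lower confidence limit for the difference in compliance for electronic versus paper questionnaires is greater than -10" (percent). No covariate or stratum is attached to this comparison. The same section plans regression adjustment for demographics and clinical characteristics, but only for comparing the preference groups.

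Section 8.1 sizes the study from an expectation that "return rates for paper questionnaires are expected to be in the region of 90% at the first post intervention time point", with a margin of 10 percentage points, 80% power and one-sided alpha of 0.05. This gives 244 randomised participants.

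Section 8.3 ends by leaving further details of methods to a statistical analysis plan, which is not at hand.

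**The concern.** When balancing factors predict the outcome, minimisation makes the true variance of the difference smaller than the simple two-proportion formula assumes. An interval from that formula is then conservative. A crude difference also leaves uncorrected any residual imbalance. Some is possible because the algorithm has a random element and because the analysed set is limited to people still expected to return a questionnaire.

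The protocol gives some reason to think the factors could matter. Section 8.3 itself names age as a confounder. Host trials differ in booklet length (four, six and four instruments in the Appendix A1 lists) and in the questionnaire of interest (EPIC-26, IPSS and EPIC-26). Sex is effectively constant, because all three listed hosts are prostate cancer trials.

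At stake is some precision in the study's one confirmatory test, and clarity about which interval decides a borderline result.

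**Working it through.** **Inputs from the protocol.** Section 8.1: paper compliance 90%, margin 0.10, one-sided alpha 0.05, power 80%, 244 randomised 1:1, so 122 per arm. Section 8.3: lower limit of a 2-sided 90% interval above -10%.

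**Assumptions.** True ePRO compliance is 90%, equal to paper, because the protocol gives no separate rate. The dependence of return on age and host trial is not given, so a range is shown.

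**1. Reproducing 244.** The Farrington-Manning formula for an unadjusted difference has restricted null proportions 0.931 and 0.831, so

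V0 = 0.931 × 0.069 + 0.831 × 0.169 ≈ 0.204

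n = (1.645 × √V0 + 0.842 × √0.18)² / 0.10² = 121.07, giving 122 per arm and 244 in total.

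The protocol does not name its formula. The unpooled Wald version gives 112 per arm (224 in total), and 224/0.92 also rounds up to 244, but no dropout allowance is stated. Both routes start from an unadjusted comparison.

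**2. Crude performance at 122 per arm.**

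Half-width = 1.645 × √(0.18/122) = 6.32 points.

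Power = Φ(0.10/√(0.18/122) − 1.645) = 83.1%.

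Exact power is 83.8% for the Wald interval and 81.9% for the Newcombe interval. Exact type I error at 80% versus 90% is 5.3% and 5.1%.

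**3. Effect of removing between-stratum variance.** Replace 0.09 per arm by the mean of p(1−p) over equal-sized strata. All stratum rates are assumed and average 90%.

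| Return rates by stratum | Half-width, points | Narrower by | Power |
|---|---|---|---|
| No variation | 6.32 | 0% | 83.1% |
| 88/92% | 6.30 | 0.2% | 83.3% |
| 85/95% | 6.23 | 1.4% | 84.0% |
| 82/88/92/98% | 6.20 | 1.9% | 84.4% |
| 80/100% (extreme) | 5.96 | 5.7% | 86.8% |

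Two cases with three equal host trials:

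- **95/90/85%:** within-host variance is (0.0475 + 0.0900 + 0.1275)/3 = 0.0883, against 0.0900 in total. The ratio is 0.98, the half-width is about 0.9% narrower, and power moves from 83.1% to 83.7%.
- **97/90/80%:** the mean is 89%, so total variance is 0.89 × 0.11 = 0.0979. Within-host variance is (0.0291 + 0.0900 + 0.1600)/3 = 0.0930. The ratio is 0.95 and the half-width is about 2.5% narrower. Power must start from the 89% baseline: Φ(0.10/√(2 × 0.0979/122) − 1.645) = 80.3% crude, against 82.0% with 0.0930.

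**4. Direction of error.** If the true standard error is r times the reported one, the crude rule's one-sided error is 1 − Φ(1.645/r). For the four prognostic rows of the table this is 4.96%, 4.76%, 4.68% and 4.05%, never above the nominal 5%.

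**5. Simulation.** This used 244 participants, two age groups by three hosts, minimisation with an assumed 80% biased coin, 4,000 runs and no true difference. Adjustment was by linear regression with robust standard errors.

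| Assumed compliance range | Half-width crude / adjusted | Power crude / adjusted |
|---|---|---|
| Flat at 90% | 6.25 / 6.27 | 83.3% / 82.6% |
| 85–95% | 6.27 / 6.26 | 82.9% / 82.7% |
| 77–99% | 6.27 / 6.10 | 84.2% / 85.0% |

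After paying for the extra model terms, adjustment gained power only where the factors were strongly prognostic. The Monte Carlo standard error of each power figure is about √(0.83 × 0.17/4000) = 0.6 points.

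**The case against.** The strongest objection is that nothing here is invalid. The sample size, margin, alpha and interval agree with one another, and a crude risk difference is transparent and defensible. This stands. A reader might infer that the interval is wider than the design warrants, or that power is lost against plan. The documents do not support that: 244 follows from an unadjusted calculation, and crude power exceeds 80%. Nor do they support reading the crude analysis as favouring ePRO, because any variance error from omitting the factors makes non-inferiority harder to claim.

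Second, no section gives return rates by age or host trial, and the three listed hosts are all prostate radiotherapy trials with overlapping questionnaires. This also stands. That the interval is too wide is conditional on the factors being prognostic, and the simulation shows a loss of up to 0.7 points of power from adjusting when they are not.

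Third, method detail is deferred to the statistical analysis plan, and the protocol does not say the minimisation factors will be excluded. This stands in part: the plan may add adjustment. But section 8.3 already fixes the estimate, interval and decision rule and places adjustment elsewhere, so its plain reading is a crude primary comparison.

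Fourth, adjustment is not free. At 90% compliance, 244 × 0.10 is about 24 non-returns, and up to six hosts are allowed. Some host-by-age cells could have complete return. This stands, and it limits the form of adjustment.

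**Conclusion.** The point holds as a modest improvement. As worded, the primary comparison does not carry the minimisation factors. If age or host trial predicts return, its interval is slightly conservative: about 0 to 2.5% in half-width in plausible cases, and at most about 1 to 2 points of power. Only the extreme 80/100% split reaches about 6% and 3.7 points. Planned power is met without adjustment, and the omission does not inflate false claims of non-inferiority.

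The reading of the text is secure. The size of the gain rests on assumed stratum rates, 90% true compliance in both arms, 122 analysed per arm and, in the simulation, an assumed biased-coin probability.

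**What to change.** In Protocol section 8.3, and in the statistical analysis plan, name the primary estimate as a risk difference adjusted for age and host trial. It can be standardised from a parsimonious model with modality, age and host trial, or be a Mantel-Haenszel difference over those strata. Compare its 2-sided 90% interval with -10%, and report the crude difference as a sensitivity analysis. State in advance how sparse host trials will be pooled, and add sex only if a mixed-sex host joins.

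The cost is a few lines of text and code. Section 6 already collects host trial, sex and date of birth at entry, and neither design nor sample size changes. The downside is a negligible loss of precision if the factors are not prognostic, and the need for a sparse-stratum rule with about 24 expected non-returns.
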